9.4 Demographic and Baseline Variables

The following baseline variables will be used to describe the trial population:

Characteristic	Prophylactic ondansetron	As-needed ondansetron	Comments
Number of subjects			
Age at enrolment, median years (25 th , 75 th centiles)			
Female sex, number (%)			
Months since JIA diagnosis, median (25 th , 75 th centiles)			
JIA Category, number (%):			
Oligoarthritis			
RF-negative polyarthritis			
Enthesitis related arthritis			
Systemic arthritis			
Psoriatic arthritis			
RF-positive polyarthritis			
Undifferentiated			
Active joint count, median (25 th , 75 th centiles)			
Physician global, median (25 th , 75 th centiles)			
Parent global, median (25 th , 75 th centiles)			
C-reactive protein, median (25 th , 75 th centiles)			
Sedimentation rate, median (25 th , 75 th centiles)			
Weight group, number (%):			
<15Kg			
15-30Kg			
>30Kg			
Previous treatment, number (%):			
None			
NSAID			
Joint injections			
Systemic corticosteroids			
DMARD			
Biologics			
Ophthalmic corticosteroids			
Known uveitis, number (%)			

9.5 Treatment Compliance

Compliance with ondansetron and methotrexate is queried at each medical visit by the attending physician (local investigator) and reported in the physician case report forms. Parents are asked to confirm in writing in the parents' questionnaire how many ondansetron tablets were given to their child with the previous dose of methotrexate.

Since this is a pragmatic trial to test effectiveness in usual medical practice, there will be no pill counts or measurement of blood medication levels as part of this trial.

10 Efficacy Analyses

The final efficacy analysis will be conducted after the last recruited trial participant has had an opportunity to be followed for 60 weeks from the date of recruitment (52 weeks plus an 8-week window of observation and data entry). The final dataset will then be verified and locked.

As per the OPT-JIA protocol (V3, 2-Sept-2020), the final analysis will be an intention to treat analysis including all randomized participants irrespective of whether they completed the trial, received or not the trial interventions, or dropped out. A secondary modified per-protocol analysis will be conducted on those subjects who received the assigned intervention for at least 3 months or stopped medications before 3 months for intolerance or toxicity.

All statistical analysis will test the null hypothesis of no differences between intervention and control groups. The a priori alternative hypothesis is that the intervention group will have better outcomes than the control group.

Logistic regression models will be used to adjust effect estimates for post-randomization imbalances in the two groups (intervention, control). Baseline variables with a p value <0.1 in the baseline comparison of intervention and control groups will be considered post-randomization imbalances and adjusted for, if any.

10.1 Primary Efficacy Analysis

The primary efficacy analysis is an intention to treat analysis comparing all subjects randomized to intervention to all subjects randomized to control. The primary efficacy analysis will include one primary endpoint and five secondary endpoints as described below.

Proportion of children who remain on methotrexate with no intolerance one year after starting methotrexate (Primary Endpoint): The primary endpoint (remain on methotrexate with no intolerance one year after starting methotrexate) has two components ("remain on methotrexate" and "no intolerance"). At every visit to the clinic the physician reports whether the patient is receiving methotrexate (MTX = 1) or not (MTX = 0). Temporarily not taking (holding) methotrexate due to intercurrent illnesses, running out of the medication, or similar reasons will not be considered a failure. If the reason for not taking methotrexate at one visit is unclear after review of the full record by the principal investigator, records will be verified with the site investigator. No intolerance means no MISS score of 6 or more points was ever recorded for that patient during the 52-week trial. Since the actual date the first methotrexate dose is given at home varies from family to family and it is not reliably recorded, we use the date of enrolment in OPT-JIA to calculate the 52 weeks of trial duration. Since OPT-JIA is a pragmatic trial and does not have study-specific visits, the visit

closest to 52 weeks is used, with a broad window of observation of 8 weeks before and 8 weeks after 52 weeks. To clearly differentiate between patients who dropped out and those who simply didn't have a visit on time, all available registry visits for all OPT-JIA participants will be provided to conduct the final analysis. Patients will be counted as successes rather than as censored if they have further registry visits beyond 52 weeks and had no failed before 52 weeks.

Our primary outcome statistic is the ratio of two proportions (relative risk, RR): the proportion of randomized children remaining on methotrexate with no intolerance one year after enrolment in the intervention group divided by the same in the control group. Subjects stopping ondansetron or methotrexate for toxicity or lack of efficacy will be counted as trial failures in calculations for the primary endpoint, irrespective of their MISS scores. A 95% CI for the RR will be calculated and the null hypothesis will be rejected if the confidence interval is entirely above 1. Considering that an interim analysis will be conducted, the alpha used in the final analysis will be 0.05 minus the alpha used in the interim analysis. As stated above, due to patient withdrawals and the fact that OPT-JIA did not have fixed-date visits, a number of patients was expected not to have a documented primary endpoint within the 52-week window, and a decision was made to use instead the Kaplan Meier estimates of the probability of success for calculations of the relative risk.

Cumulative incidence of methotrexate intolerance within one year: The Kaplan Meier survival analysis estimate of the cumulative incidence of a MISS score of 6 or more points within 52 weeks of study enrollment, as defined above. Kaplan-Meier curves will be constructed separately for intervention and control groups and the curves will be compared using the log-rank test.

Cumulative incidence of attainment of inactive disease within one year: The Kaplan Meier survival analysis estimate of the cumulative incidence of attainment of inactive disease within 52 weeks of study enrollment. At every visit to the clinic the pediatric rheumatologist is asked for current disease status (inactive disease = 1, active disease =2). Inactive disease is defined as per the Wallace criteria: no joints with active arthritis; no fever, rash, serositis, splenomegaly, or generalized lymphadenopathy attributable to JIA; no active uveitis (by SUN definition, <1 cell in field sizes of 1 mm by a 1-mm slit beam); ESR or CRP level within normal limits in the laboratory where tested or, if elevated, not attributable to JIA [If not tested because there was no clinical indication, it is assumed to be normal]; physician's global assessment of disease activity (PGA) score of best possible on the scale used (0 in a 21 point scale from 0=inactive to 10=very active disease); duration of morning stiffness of 15 minutes or less. Additionally: no enthesitis. Active disease means any of the above disease manifestations is present, or a PGA of 0.5 or more. Kaplan-Meier curves will be constructed separately for intervention and control groups and the curves will be compared using the log-rank test.

Cumulative incidence of starting a biologic medication within one year: The Kaplan Meier survival analysis estimate of the cumulative incidence of starting a biologic medication within 52 weeks of study enrollment. At every visit to the clinic the physician is asked if the patient is receiving any biologic medication (Yes = 1, No = 0). If the answer is yes, the physician selects the relevant medication from a list or enters the name of the medication. Kaplan-Meier curves will be constructed separately for intervention and control groups and the curves will be compared using the log-rank test.

Mean quality of life scores in the Quality of My Life scale 4-8 months after starting methotrexate: The arithmetic mean of the score in the Quality of My Life scale answered by the patient. If more than one score is available 4-8 months after enrollment, the score closest to 26 weeks is used. All patients considered mature enough to understand the questions (by their parents) are asked: "Some

of the children who come to see us feel that their life is not that great, while others think that their life is O.K. How about you?" (The patient then selects the relevant answer in a 21-point horizontal rating scale from The worst = 0, to The Best = 10). Then, the patient is asked: "Considering my HEALTH, my life is..." and the patient again selects the relevant answer in a 21-point horizontal rating from The worst = 0, to The Best = 10). The answer to the second question is the score of interest. The mean scores of intervention and control groups will be compared with a two-sample two-tailed t-test.

Mean scores in the MISS questionnaire 4-8 months after starting methotrexate: The arithmetic mean of the score in the Methotrexate Intolerance Severity Score questionnaire answered by the parent. If more than one score is available 4-8 months after enrollment, the score closest to 26 weeks is used. The score is the sum of 12 items, each scored as 0= No complaints, 1= Mild, 2= Moderate, 3= Severe), for a total possible score of 36 points. The MISS questionnaire is included in the Case Report Forms appended to this Statistical Analysis Plan. The mean scores of intervention and control groups will be compared with a two-sample two-tailed t-test.

Mean scores and between groups p-values at 26 weeks are exploratory and will be interpreted with caution for two reasons: 1) OPT-JIA has no fixed-time visits and some patients may not have scores at 26 weeks; 2) The Quality of My Life score will not be available for patients deemed too young by their parents to understand the question.

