8.4 Missing Data

(ICH E3; 9.7.1, 11.4.2.2. ICH E9;5.3. EMA Guideline on Missing Data in Confirmatory Clinical Trials)

During ongoing quality control of data entered in the study database, data from a study visit is reviewed by the study registry coordinator within 2 weeks of being entered and queries are sent to the site regarding any missing or apparently spurious data. Once these queries are answered satisfactorily, the data for that visit is locked. Only data contained in locked visits will be used for trial analyses.

In preparation for the interim and final analyses, the study statistician will perform further examination of the data for outlier values. Values outside a plausible range (e.g. an erythrocyte sedimentation rate >200 mm/h) will be converted to missing values.

After receiving the locked study dataset for the final analysis and dealing with values outside a plausible range, missing values will be imputed if needed using multiple imputations by chained equations.

Missing MISS questionnaire scores will not be imputed. Subjects with missing MISS questionnaire scores while still receiving methotrexate will be considered as censored as of the last available visit with a valid MISS score.

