8.5.5 Analysis Methods to Minimize Bias

Although OPT-JIA is not a blinded RCT, the two components of the primary endpoint are robust and unlikely to be influenced directly by the OPT-JIA investigators or the statisticians. Whether a patient is receiving methotrexate or not is a verifiable occurrence not under their control, and intolerance is defined directly by the parents by answering a validated questionnaire. Further, there is no pharmaceutical sponsor for OPT-JIA and the medications being tested have been marketed as generic medications in Canada for >20 years, making bias introduced by a pharmaceutical sponsor not possible.

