8.5.8 Practical Measures to Minimize Bias

The interim analysis is conducted by a PhD student in the Department of Statistics and Actuarial Science at Simon Fraser University, working under the direct supervision of the study statistician. Neither the statistician nor the student has a financial stake in the outcome of the trial. They receive only the data necessary to conduct the analysis and confirm its accuracy.

The results of the interim analysis are presented to the DSC by the study statistician and the DSC is charged with making a recommendation to the PI as to the advisability of continuing the trial.

OPT-JIA does not have a pharmaceutical sponsor and all medications tested in the trial are medications currently marketed in Canada and available as generic medications. The study PI, [name], serves as the trial sponsor in Health Canada submissions.

As per the OPT-JIA DSC Charter, [name] will consider the recommendation of the DSC. If the recommendation is to continue the trial to attain the newly calculated sample size, [name] will consider the feasibility of this approach given available study funding and the observed recruitment rate. No information will be made public until a final determination is made.

Because the intervention requires all parties in the trial to act differently from the control, there is no blinding in the trial, and hence no need for additional measures during the statistical analysis to preserve blinding.

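### Whether a methotrexate gap counts as a failure rests partly on an unmasked judgement of the reason, which SAP 8.5.5 does not acknowledge

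*SAP*

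**What the plan says.** The primary endpoint is remaining on methotrexate with no intolerance at 52 weeks. SAP 8.5.3 makes stopping methotrexate a failure. SAP 10.1 then separates holding from stopping by the reason: a temporary hold "due to intercurrent illnesses, running out of the medication, or similar reasons will not be considered a failure". It gives no gap length and no closed list.

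Unexplained gaps go through two steps in 10.1. The principal investigator reviews the whole record. The SAP continues: "If the reason for not taking methotrexate at one visit is unclear after review of the full record by the principal investigator", then "records will be verified with the site investigator". Section 10.1 names the two roles separately, so the first is the study's principal investigator, whom 8.5.8 identifies as the sponsor in regulatory submissions.

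A further rule in 10.1 also turns on the reason: "Subjects stopping ondansetron or methotrexate for toxicity or lack of efficacy will be counted as trial failures".

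On masking, 6.3 states that there is none, and the table in 6.4 records ondansetron use and dose at every visit. Section 8.5.5 defends the open-label endpoint as follows: "Whether a patient is receiving methotrexate or not is a verifiable occurrence not under their control". There, the pronoun refers to the investigators and statisticians.

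**The concern.** In an open-label trial, masked classification of the endpoint is one of the main protections still available. Here the same observation, a child not taking methotrexate at a visit, can be a failure or not depending on a reason that someone must assign. The two people named for that task can see the arm, and one of them is the sponsor. Section 8.5.5 presents this component as beyond the investigators' influence. A later reader who questions the result would be pointed to 8.5.5, which does not address how the reason is assigned. At stake is the credibility of the primary comparison and, if reclassification leaned one way, its type I error.

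**Working it through.** **1. Sections side by side**

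- *On or off drug (8.5.5).* Described as verifiable and not under the investigators' control. For the bare status this is arguable, although 9.5 equates the attending physician who asks about the drug with the local investigator.
- *Why off drug (10.1).* Decides hold or stop. The category of similar reasons is open-ended.
- *Who looks (10.1, 8.5.8).* The principal investigator, who is the sponsor, and then the site investigator. The SAP does not say who makes the final classification.
- *Can they know the arm (6.3, 6.4)?* Yes. There is no masking and ondansetron use is in the record. The SAP does not hide the allocation for this step.

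So 8.5.5 speaks to the status, while failure turns on the reason.

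**2. The plan's own sample size, to set the scale**

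Section 7 gives 79 evaluable per group (50% v 75%, 90% power, p<0.05) and 176 in total.

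- Log relative risk, two-sided 0.05 assumed. Variance terms: null 2(1−0.625)/0.625 = 1.2; alternative 0.25/0.75 + 0.5/0.5 = 1.3333.
- n = (1.96√1.2 + 1.2816√1.3333)² / (ln 1.5)² = 80.0 per group, close to 79.
- 2 × 79 / 0.90 = 175.6, rounded up to 176, as stated.

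**3. What a lopsided reclassification would do (assumed shifts)**

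Assumptions: true success of 50% in both arms, binary outcomes in place of Kaplan-Meier estimates, and alpha 0.05 − 0.0045 = 0.0455 (8.5.6), so z = 2.00. Benefit is claimed if ln(x₁/x₀) − 2.00·√(1/x₁ − 1/n + 1/x₀ − 1/n) > 0, with x₁ and x₀ the successes on intervention and control. The exact probability of that event is:

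| Net shift favouring intervention | 79 per arm | 22 per arm |
|---|---|---|
| none | 2.3% | 1.5% |
| 2 points | 4.1% | 2.2% |
| 5 points (about 4 of 79) | 8.6% | 3.5% |
| 10 points | 23.0% | 7.4% |

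The 22 per arm is an assumed even split of the 27 + 17 = 44 children described for the interim in section 15.

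**4. How much room there is**

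In the cohort cited in 8.5.4, 59 of 142 children became intolerant and 11 stopped for other reasons: 11/142 = 7.7%, or 0.077 × 79 ≈ 6 children per arm. Stops without intolerance are the main group that could be re-read as holds, and only the unclear ones among them matter. On that cohort a 10-point shift from this source is not possible, and 5 points would use about two-thirds of the group (5/7.7 = 0.65). The cohort gives no figure for the opposite error, true holds read as stops.

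**The case against.** Several points on the other side are sound.

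- A reader might infer that the sponsor alone decides who fails. The SAP does not say so: the principal investigator reviews, and what stays unclear is checked with the site. That check is a safeguard against error, but not against knowledge of the arm, because the site is unmasked too.
- Section 8.5.5 is hedged. It calls direct influence unlikely rather than impossible, and bare methotrexate status can be verified. Section 10.1 also supplies all registry visits, so later visits may show whether the drug was resumed. The SAP does not make resumption the rule.
- A reader might take 8.5.8 as rejecting all masking. Its words are "no need for additional measures during the statistical analysis to preserve blinding", which concern the statistical analysis and say nothing of endpoint review.
- It is tempting to extend the point to other data decisions. The documents do not support that. The outlier example in 8.4 is a sedimentation rate, which is not part of the primary endpoint. Per-protocol membership already has a rule in 9.3 and 10.2. Eligibility exclusions in 9.3 are limited to exceptional circumstances, and no decider is named.
- One child can tip a borderline result: with 39/79 control successes, 51/79 on intervention gives a lower limit of 0.986 and 52/79 gives 1.008. Every trial has such a margin, so this is no evidence of bias.

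The core remains: failure depends on an attributed reason, assigned without masking.

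**Conclusion.** The concern holds in this limited form. The hold-or-stop classification is an unmasked judgement within the primary endpoint, made under an open-ended definition, and 8.5.5 is wrong to the extent that it implies no investigator judgement enters the methotrexate component.

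The size of any bias is unknown, because the SAP gives no number of unclear gaps. The type I error figures depend wholly on assumed shifts, equal true rates of 50% and binary outcomes. On the SAP's own cited cohort, the stops open to being re-read as holds are few. Nothing in the document shows that any classification has been biased, and a reader should not infer it.

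The amendment should be made before the final dataset is locked.

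**What to change.** In 10.1:

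- The registry coordinator, who already checks visit data under 8.4, prepares an extract for the methotrexate review without allocation and ondansetron fields.
- The trial team writes its definition of a hold before the review starts. Each gap is classified against it, by a named role, and logged before the arm is merged.
- Ondansetron stops that count as failures under 10.1 are assessed in a separate step, since they cannot be judged on an extract without those fields.
- Cases already classified at the interim are flagged as reviewed unmasked.
- A sensitivity analysis counts every unclear gap as a failure in both arms.

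In 8.5.5, state that the reason for not taking methotrexate involves investigator judgement, and refer to the masked review.

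The cost is SAP wording, one additional extract, a decision log and one additional analysis. Masking will be imperfect for children at the principal investigator's own site, and where the reason comes from an unmasked site physician. The sensitivity analysis is there partly for that.

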8.5.3 Scope of Adaptations

The trial steering committee, with approval from the DSC, elected to conduct the interim analysis at an earlier stage of the trial than initially planned. Because of challenges relating to the COVID19 pandemic and other reasons, recruitment into the study had been much slower than anticipated, and there were concerns that the initial planned sample size might be unattainable within a reasonable time frame. The interim analysis was rescheduled to take place using all available enrolments into the study as of September 30, 2023.

Because the analysis would be based on a much smaller fraction of the intended sample size, the OPT-JIA PI and the study statistician proposed, and the DSC agreed, to base the analysis on the confidence interval for relative risk computed using the ratio of two estimates of the probability of successful trial completion from independently estimated Kaplan Meier curves. These estimates would better account for the partial information available from patients who did not have sufficient time in the study to complete the 52-week observation period.

To make use of all available information from patients who had not completed the trial yet, the definition of the primary end point was modified as follows. Visit times were shown in weeks since enrolment in OPT-JIA. We used 52 weeks to represent the 1-year visit as required for determining success. Failure was determined to have occurred if any of the criteria for failure -- stopping methotrexate or experiencing intolerance -- were observed during any visit up to and including 52 weeks. Success was determined to have occurred if no failure criteria were met at or before 52 weeks, and the patient had at least one visit at or after 52 weeks. All other patients were considered censored as of the time of their last visit; i.e., they were known not to have failed yet, but they had not yet provided a visit at or beyond 52 weeks to declare success.

The second adaptation was the use of the O'Brien-Fleming adjustment to type 1 error rate for the calculation of the confidence interval in the interim analysis [17]. This adjustment resulted in calculation of a 99.55% confidence interval for the interim analysis instead of the 95% mentioned in the protocol. The rationale being that both the interim and the final analysis together would then have a 5% chance of a positive result if the intervention is no more effective than control.

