With the agreement of the Steering Committee and the Data and Safety Committee, the interim analysis took place at an earlier stage than initially specified because of the slow enrolment into the study. The interim analysis was planned by [name] with the assistance of [name] and discussed with the PI, [name], in March 2023. It was discussed and approved at the steering committee call of April 21, and at the Data and Safety Committee call on May 8, 2023, and further confirmed with the DSC chair via email on October 5, 2023. The approved plan was to extract information from the REDCap database on September 30, and this was postponed to October 6, to allow time for responses to remaining queries to be verified by site principal investigators. The sample sizes for the interim analysis were smaller than had been expected, and hence there were only 27 patients on whom success or failure had been definitively determined at the time the interim analysis was conducted with data extracted on October 6th, 2023. There were an additional 17 participants who were still on the trial, with at least one follow-up visit but not yet to their 52-week visit. We therefore used the Kaplan-Meier (KM) statistical analysis technique separately in each group to estimate the probability of success in each group in a way that would make some use of the partial information provided by the patients with incomplete follow-up periods.

We used the KM method to estimate the probability of success at 52 weeks and formed the relative risk (RR) by dividing the estimated probability for the intervention group by the estimated probability for the control group. The statistical properties of the RR are better expressed on the log scale, so we computed the log of this ratio, which is equivalent to the difference between the two logged survival probabilities. We computed the standard error for this difference using the separate standard errors for each logged survival probability and computed the confidence interval on this log scale using the standard normal (Wald) method. The same KM methods will be applied for the final efficacy analysis.

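### SAP 10.1 scores the final primary endpoint by rules that disagree, and its further-visit success rule contradicts 8.4 on missing MISS scores

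*SAP*

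**What the plan says.** Section 10.1 holds three statements on how a child is scored at one year.

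- **Window.** The visit "closest to 52 weeks is used, with a broad window of observation of 8 weeks before and 8 weeks after 52 weeks". The window table in 6.4 agrees: Month 12 is day 364 with bounds 308 and 420. Section 10 times the final analysis so that the last child can be "followed for 60 weeks from the date of recruitment (52 weeks plus an 8-week window of observation and data entry").
- **52-week limit.** No intolerance means "no MISS score of 6 or more points was ever recorded for that patient during the 52-week trial".
- **Further visit.** Children are "counted as successes rather than as censored if they have further registry visits beyond 52 weeks and had no failed before 52 weeks". No MISS score, methotrexate status or upper time limit is attached to that visit.

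Other sections bear on the same child.

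- 8.4 does not impute MISS. A child still on methotrexate with a missing score "will be considered as censored as of the last available visit with a valid MISS score".
- 8.5.3, written for the interim, counts failures at visits up to and including week 52: "Success was determined to have occurred if no failure criteria were met at or before 52 weeks", together with at least one visit at or after week 52.
- 10.1 moves to Kaplan-Meier estimates because "a number of patients was expected not to have a documented primary endpoint within the 52-week window". Section 9.3 says the same, and section 15 adds: "The same KM methods will be applied for the final efficacy analysis".
- 9.2 sets the derived variable INTOLERANCE to 1 for any recorded MISS of 6 or more, without a week limit.

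No section ranks these rules.

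**The concern.** The primary endpoint needs one event rule and one censoring rule. A Kaplan-Meier estimate at week 52 treats a child coded as a success as known to be event-free to week 52. A child censored at week 20 contributes nothing after week 20. If the SAP allows both codes for one history, the primary relative risk depends on a choice made while programming. In an open-label trial that choice should be fixed in writing before the data are analysed.

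The conflict over missing MISS is the more serious part. In the planning cohort cited in 8.5.4, most failures were intolerance, which only the MISS score detects. A clinic visit without a MISS can show that methotrexate continues, but it cannot show that the child tolerates it.

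**Working it through.** **1. Units.** 308/7 = 44, 364/7 = 52 and 420/7 = 60, so the 6.4 window and the 10.1 window are the same: weeks 44 to 60.

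**2. Share of failures that only MISS can show.** From 8.5.4: 142 children, 59 intolerant, 11 stopped for other reasons. Failures = 59 + 11 = 70, and 142 − 70 = 72 (50.7%), as the SAP states. Share due to intolerance = 59/70 = 84%.

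**3. Histories scored by each rule.**

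| History | Closest visit, weeks 44–60 | 8.5.3 / 52-week limit | Further visit (10.1) | 8.4 |
|---|---|---|---|---|
| Well at week 42, MISS 10 at week 55 | failure if that MISS counts | success | success | not involved |
| On methotrexate, last MISS at week 20, visit at week 58 without MISS | no score to read | success (any visit at or after week 52) | success | censored at week 20 |
| No failure, last visit at week 46 | success | censored at 46 | censored | not involved |

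The second row is a direct contradiction between 10.1 and 8.4. The success clause in 8.5.3 shares it, because it also asks only for a visit.

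**4. Size of the 8.4 conflict.** The SAP gives neither the MISS missing rate nor the actual visit spacing, so this is a simulation under assumptions.

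Inputs from the SAP: success 50% v 75% (section 7), visits every 1–4 months (5.2, 6.1), 10% dropout (section 7), 59/70 of failures visible only by MISS (8.5.4).

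Assumed: constant hazard, h = −ln(S)/52 with S = 0.50 or 0.75; gaps uniform over 1–4 months; dropout uniform over the year; failure seen at the next visit that can show it; 300,000 children per arm. RR = KM(52) intervention / KM(52) control.

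| MISS missing | Further-visit rule | 8.4 with 52-week limit |
|---|---|---|
| none | 0.772/0.540 = 1.43 | the same |
| stops permanently in 10% | 0.783/0.559 = 1.40 | 0.769/0.533 = 1.44 |
| stops permanently in 20% | 0.793/0.579 = 1.37 | 0.765/0.525 = 1.46 |
| at random, 10% of visits | 0.777/0.548 = 1.42 | 0.777/0.547 = 1.42 |
| at random, 20% of visits | 0.785/0.559 = 1.40 | 0.784/0.556 = 1.41 |

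Repeating this with other seeds and small changes of set-up gives 1.40–1.41 (1.37–1.38) for the further-visit rule and 1.44–1.45 (1.45–1.47) for 8.4 under permanent stopping. Random missingness matters little because most children have a later valid MISS. With 1–4-month gaps, only 0.5–2.6% of children have a visit after week 52 but no valid MISS from then on. With 4-monthly visits the difference under random missingness is at most about 0.01.

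**5. Size of the window conflict.** Under the same assumptions with no missing MISS, 3.8% of control and 2.3% of intervention children first show failure at a closest visit in weeks 52–60. With 88 per arm: 0.038 × 88 = 3.3 and 0.023 × 88 = 2.0, about 5 of 176 children. With 4-monthly visits it is 5.8% and 3.4%, or about 5 and 3 children.

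**The case against.** The strongest reply is that the SAP does settle the event rule. Sections 8.5.3, 9.3, 10.1 and 15 all point to Kaplan-Meier at week 52, and 9.2 times each visit by its actual date. A MISS of 10 at week 55 is then an event at week 55 and leaves the estimate at week 52 unchanged. The extra 8 weeks in section 10 fit simply waiting for a visit at or after week 52. This reading is the best supported. A reader might infer that a MISS in weeks 52–60 is left undefined. The documents do not support that: the score falls outside the 52-week limit, and what contradicts this is a closest-visit sentence and table row that were never reconciled with the Kaplan-Meier definition.

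A reader might also compare 1.43 with the planned 75/50 = 1.50 and infer that the 52-week rule is biased and that the MISS period should run to week 60. That gap arises because failures are seen at the next clinic visit and are compared here with an assumed onset time. The SAP's endpoint is a score recorded by week 52. Moving the limit would redefine the primary endpoint after an open-label interim. Nor does the SAP document visit spacing that differs by arm, so a bias in favour of the intervention cannot be claimed.

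On missing MISS, it can be said that the further-visit rule is meant for children who merely came late, that 8.4 is the more specific rule, and that site queries will recover many scores. This is a sensible intention, but 10.1 does not say it. Its sentence covers every child with a later visit, and the two sections still give different answers for the same history.

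**Conclusion.** The concern holds as a contradiction in the primary endpoint's scoring, of modest size. Section 10.1 taken literally scores an unmeasured MISS as tolerance where 8.4 censors, and its window sentence conflicts with the 52-week Kaplan-Meier definition.

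The first conflict moves the relative risk by about 0.04 to 0.09, with the further-visit rule nearer to no effect, if MISS stops permanently in 10–20% of children. It moves it hardly at all if scores are missing at random visits. The second would rescore roughly 4% of control and 2% of intervention children.

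These sizes rest on 75% v 50% success, a constant hazard, equal visit spacing in both arms and missing rates that the SAP does not give. The contradiction itself rests on the text alone. It should be corrected, but it does not threaten the trial.

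**What to change.** Set the following before the final data are analysed, and leave 8.5.3 as the record of the interim.

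1. State in 10.1 that the 8.5.3 event definition governs the final analysis: failure at any visit up to and including week 52, Kaplan-Meier estimate at week 52. State that the weeks 44–60 window in 10.1 and 6.4 is descriptive or only sets the data cut.
2. State that 8.4 governs missing MISS. Registry visits after week 52 make a success only if they show methotrexate ongoing (or on a temporary hold as 10.1 already allows) and a valid MISS is available at or after week 52. Otherwise the child is censored at the last valid MISS. Step 1 alone does not achieve this, because the 8.5.3 success clause also asks only for a visit.
3. Give INTOLERANCE in 9.2 the same 52-week limit.
4. Report as sensitivity analyses only: the closest-visit rule with its MISS counted, and an interval-censored estimate.

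The Kaplan-Meier and Wald method of section 15 and the sample size stay as they are. The cost is SAP wording, minor programming and some more censored children, so slightly wider intervals.
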